5.2.3.2. Analysis Methods

Analysis of duration of disease control will be based on Kaplan-Meier method, median DODC with 95% CI will be estimated. The Kaplan-Meier duration of disease control curve will be plotted.

5.2.4. Overall Survival

5.2.4.1. Definition

Overall survival is measured from the date of first siltuximab/placebo (siltuximab-naïve subjects) treatment to the date of death due to any cause. Subjects who withdraw consent from the study or are lost to follow-up will be censored at the time of withdrawal or lost to follow-up. Subjects who are still alive at the cutoff date for the analysis will be censored at the last known alive. The date of last known alive will be determined by the maximum collection/assessment date from among selected data domains within the clinical database.

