**11.4 Efficacy and Patient-reported Outcomes Analyses****11.4.1 Disease Control**

Investigator assessment of disease control for all treated subjects will be analyzed. Specifically, the proportion of previously responding subjects and siltuximab-naïve subjects who maintain disease control will be summarized. The duration of disease control, defined as the time from the first siltuximab administration to disease progression as assessed by the investigator, will also be summarized.

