2.2. Study Data to Be Included in Analysis Tabulation

Subjects treated in the long-term safety extension study of CNTO328MCD2002 were previously enrolled in sponsor-initiated studies of MCD, therefore demographics, baseline characteristics, and prior systemic therapy data will come from parent study of C0328T03 or CNTO328MCD2001. Overall treatment exposure, safety evaluations (i.e., adverse events), and overall survival will be based on parent study and extension study. The data included in these overall summaries are from the start of C0328T03 or CNTO328MCD2001 to the end of CNTO328MCD2002.

Due to quite different schedules in laboratory assessment and vital sign collection between parent study and long-term safety extension study, safety evaluation through laboratory assessment and vital signs will focus on long-term safety extension study of CNTO328MCD2002. Similarly, immunogenicity analyses will also be based on long-term safety extension study.

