2.4. Siltuximab Treatment Date

Siltuximab treatment date is the date on which a subject actually received siltuximab (partial or complete) administration.

For subjects who previously received siltuximab treatment, the first siltuximab treatment date is defined as the earliest date of non-zero dose of siltuximab administration from study C0328T03 or CNTO328MCD2001. The last study treatment date is defined as the latest date of non-zero dose of siltuximab administration from CNTO328MCD2002.

For subjects who were siltuximab-naive, the first study treatment date is defined as the earliest date of non-zero dose of siltuximab from study CNTO328MCD2002. The last study treatment date is defined as the latest date of non-zero dose of siltuximab administration from study CNTO328MCD2002.

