2.7. Analysis Sets

Safety population is defined in this study. The safety population will include subjects who have received at least 1 administration of siltuximab treatment (partial or complete). This analysis population will be used for all analyses.

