5.2.3. Duration of Disease Control

5.2.3.1. Definition

For subjects who had/experienced disease control, duration of disease control (DODC) is defined as the time from the first siltuximab administration to disease progression as assessed by the investigator. Subjects with disease control are subjects who had stable or better response assessed by the investigators. Subjects without disease progression will be censored at the date of last disease assessment. Note that disease control was only collected in long-term safety extension study of CNT0328MCD2002.

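### Overall survival runs from the first parent-study dose, but only subjects who reached the extension are analysed, so ordinary Kaplan-Meier overstates 3- to 6-year survival from first treatment

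*SAP*

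**What the plan says.** **Time origin for survival.** SAP 5.2.4.1: "Overall survival is measured from the date of first siltuximab/placebo" treatment, with placebo applying to siltuximab-naive subjects. SAP 2.4 sets the first siltuximab date of previously treated subjects at "the earliest date of non-zero dose of siltuximab administration from study C0328T03 or CNTO328MCD2001". SAP 2.2 agrees: "and overall survival will be based on parent study and extension study".

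**Who is analysed.** SAP 2.2 describes the cohort: "Subjects treated in the long-term safety extension study of CNTO328MCD2002 were previously enrolled in sponsor-initiated studies of MCD". SAP 2.7 defines a single safety population and adds: "This analysis population will be used for all analyses".

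**Estimator.** SAP 5.2.4.2 plans Kaplan-Meier for the median and for the 3-, 4-, 5- and 6-year rates with 95% confidence intervals. Neither document mentions delayed entry, left truncation or a conditional reading.

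**Duration of disease control (DODC).** Protocol 11.4.1 has it "defined as the time from the first siltuximab administration to disease progression as assessed by the investigator", and SAP 5.2.3.1 uses the same origin. For naive subjects SAP 2.4 says "the first study treatment date is defined as the earliest date of non-zero dose of siltuximab from study CNTO328MCD2002". SAP 5.2.3.1 also says: "Note that disease control was only collected in long-term safety extension study". SAP 2.2 does not list DODC among the analyses that combine parent and extension data.

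**Protocol on survival.** Protocol 11.4.3 starts the clock at the first study siltuximab dose, most naturally read as the first dose in this study. It censors subjects lost to follow-up when last known alive. The SAP censors them at the time of loss.

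**The concern.** A subject who died during the parent study, or before the first extension dose, cannot be in the dataset. Each analysed subject nevertheless contributes the interval from first parent-study dose to first extension dose as follow-up at risk. Deaths in that interval are impossible by construction, so the early part of the curve is held up and every later estimate is inflated relative to survival from first treatment.

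The interval is not negligible. The amendment log for INT-2 (June 2012) says that nearly all subjects had well over 48 weeks of treatment at entry. Protocol 1.1.2.1 reports C0328T03 exposure with a median of 331 days and a maximum of 1148 days. SAP 4.3 plans exposure bands up to more than 8 years, although the cutoff falls about 6 years after first enrolment, so delays above 2 years are foreseen for some subjects.

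For DODC, SAP 2.4 most naturally puts the origin for previously treated subjects in the parent study. Progression was recorded for this endpoint only in the extension, and inclusion criterion 4 bars prior progression on siltuximab (with an exception for placebo subjects shortly after crossover). The same problem then arises. Naive subjects start in the extension, so a pooled curve would also mix two origins.

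There is no hypothesis test, so no error rate is affected. But duration of disease control and survival form a secondary objective, and Amendment INT-4 extended the study partly to report long-term survival. Unlabelled 3- to 6-year rates would be taken as survival from first treatment.

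**Working it through.** The plan gives no survival rate to reproduce, and its sample size is not statistically derived. The calculation therefore shows the bias over stated assumptions.

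**Set-up.** Let T be survival from first parent-study dose (exponential, rate λ) and D the delay from that dose to the first extension dose, independent of T. A subject is analysed only if T > D. With no censoring before the largest delay, ordinary Kaplan-Meier at any t beyond it estimates

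P(T > t | T > D) = S(t) / E[S(D)].

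For D uniform on (a, b), E[S(D)] = (e^(−λa) − e^(−λb)) / (λ(b − a)).

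**Assumed inputs.** True 5-year survival of 80% (λ = −ln 0.80/5 = 0.0446 per year) or 70% (λ = 0.0713), with three ranges for D.

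| Delay (years) | E[S(D)], true 80% | Reported 5-year rate | E[S(D)], true 70% | Reported 5-year rate |
|---|---|---|---|---|
| 0.25-1 | 0.9725 | 0.80/0.9725 = 82.3% | 0.9565 | 0.70/0.9565 = 73.2% |
| 0.5-2 | 0.9459 | 84.6% | 0.9151 | 76.5% |
| 1-3 | 0.9149 | 87.4% | 0.8678 | 80.7% |

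**Mixture tied to the documents.** At most 23 of the 75 subjects can come from the 23 Castleman's subjects in C0328T03. Give them delays shaped to Protocol 1.1.2.1 (half uniform on 0-331 days, half on 331-1148 days) and give the other 52 each range in turn.

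| Delay of the other 52 (years) | True 80% | True 70% | 95% CI coverage at n = 75 (80% / 70%) |
|---|---|---|---|
| 0.25-1 | 82.9% | 74.1% | 95% / 90% |
| 0.5-2 | 84.5% | 76.4% | 91% / 80% |
| 1-3 | 86.5% | 79.3% | 81% / 61% |

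Coverage is for the log-log interval at 5 years, over 40,000 simulated trials.

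**All four landmarks**, mixture with 0.25-1 year, by simulation:
- True 3/4/5/6-year rates of 87.5/83.7/80.0/76.5% are reported as 90.6/86.7/82.9/79.3%.
- True rates of 80.7/75.2/70.0/65.2% are reported as 85.4/79.6/74.1/69.0%.

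**Cross-check from the INT-2 statement.** Put 90% of subjects at exactly 48 weeks (0.92 years) and 10% at zero:
- 0.80 / (0.1 + 0.9 × 0.80^(0.92/5)) = 83.0%
- 0.70 / (0.1 + 0.9 × 0.70^(0.92/5)) = 74.2%

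**Alternatives.** In the 0.25-1 year mixture with 3.5-6 years of follow-up after entry, delayed-entry Kaplan-Meier returns 80.0% and 70.1%, and starting at the first extension dose returns 80.0% and 70.0%. Delayed entry needs subjects at risk early: with delays of 1-3 years for everyone, nobody enters before year 1 and it returns 83.6% for a true 80%.

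**Median survival.** The true medians here are 5 × ln 2/0.2231 = 15.5 years and 5 × ln 2/0.3567 = 9.7 years. Both lie beyond most follow-up, so no effect on the median is claimed.

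**DODC, parent-study origin.** Assume a true median of 3 years, 6 years of follow-up after entry, and a naive share from 0 to 49% (Protocol 3.1 expects most subjects to be on siltuximab at entry). The estimated median is 3.8 down to 3.5 years with the 0.25-1 year mixture, and 4.7 down to 3.8 years with the 1-3 year mixture. At non-zero naive shares these move by about 0.1 year with how the mixture is applied.

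**The case against.** **The curve is valid for a conditional quantity, and nothing is tested.** The SAP says its subjects came from parent studies and describes the entry criteria. It does not claim to estimate survival for everyone who started siltuximab. This stands as far as it goes: with a clear label the curve would be correct. The plan has no such label, and rates at fixed years from first treatment invite the other reading.

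**The analysis set might include all parent-study subjects.** SAP 2.7 does not itself say the dose must be in the extension, and a wider set would remove the bias. But SAP 2.2 and 4.2, Protocol 11.1, and a cap of 75 against about 78 planned in CNTO328MCD2001 alone all point to extension-treated subjects.

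**The size is assumed.** This is correct. The documents give neither delays nor survival rates. The C0328T03 exposure figures are an early snapshot of a group that included unresectable localized disease. With short delays the bias stays within sampling error.

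**Delayed entry is noisy at n = 75.** This also stands. In the six mixtures without censoring, its root-mean-square error at 5 years exceeded that of the SAP method (for a true 80%, 7.0 against 5.2 points with 0.25-1 year, and 9.3 against 7.6 with 1-3 years). If entry also selects on non-progression, it removes only part of the bias. It therefore belongs in a secondary analysis. Starting at the extension dose was unbiased under a constant hazard, with lower error than the SAP method in all six mixtures, though it answers a different question when the hazard changes over time.

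**The DODC origin is ambiguous.** It is, and under an extension origin the flaw disappears. That ambiguity still has to be resolved.

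**Conclusion.** The concern holds. As written, the SAP counts time in which death was impossible as time at risk, and its 3- to 6-year survival rates are biased upward if read as survival from first treatment. The direction follows from the definitions.

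The size rests on assumed delays, an exponential survival curve, and independence of delay and survival. Under the mixtures, the 5-year overstatement is about 3 to 6.5 points for a true 80% and about 4 to 9 points for a true 70%. Short delays leave the nominal interval nearly intact; delays of 1-3 years do not.

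For DODC the same bias applies only on the parent-study reading of the origin, which is the more natural one under SAP 2.4 but is not stated. The SAP's survival origin also departs from the natural reading of Protocol 11.4.3. The difference in censoring of subjects lost to follow-up is a smaller inconsistency.

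This should be corrected before the final analysis. It affects how a descriptive secondary result is interpreted, not a test.

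**What to change.** In SAP 5.2.3 and 5.2.4:

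- Start the main survival and DODC analyses at the first CNTO328MCD2002 dose, presented separately for previously treated and siltuximab-naive subjects. State the DODC origin explicitly.
- If time since first siltuximab is also wanted, report it as a secondary analysis using delayed-entry Kaplan-Meier. The risk set opens at the first extension dose, and the curve is conditioned on a prespecified start time with an adequate risk set. Label it as conditional on reaching the extension.
- As a minimum, if the parent-study origin and ordinary Kaplan-Meier are kept, put that label on every survival rate and curve.
- Reconcile the survival origin with Protocol 11.4.3, and censor subjects lost to follow-up when last known alive, as that section does.
- State that selection on response and tolerability at entry (Protocol 4.2 and 4.3) remains under every option.

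The cost is SAP wording and one entry-date variable already held; no new data are needed. The price is less favourable curves, shorter follow-up from time zero, thin early risk sets in any delayed-entry analysis, and results still conditional on selection into the extension.

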#### **9.3.3 Survival**

For subjects who discontinue study agent, survival status will be assessed twice per year until the subject has been lost to follow-up or has withdrawn consent for the study, or the 6-year data cutoff; whichever occurs first.

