**11.4.3 Overall Survival**

Overall survival is defined as the time between the first study siltuximab administration and death. Subjects who died, regardless of the cause of death, will be considered as an event. Subjects who withdraw consent from the study will be censored at the time of withdrawal. Subjects who are still alive at the cutoff date of the final analysis will be censored at the date of last known alive. All subjects who are lost to follow-up before the 6-year data cutoff will be censored at the date they are last known to be alive.

The Kaplan-Meier method will be used to estimate the distribution of overall survival. Median overall survival with 95% CI will be provided. In addition, the Kaplan-Meier overall survival curve will also be provided.

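### The SAP censors overall survival for subjects lost to follow-up at an undefined loss date, where the protocol uses the date last known alive; if the loss date is later, the survival estimates can only stay equal or rise

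*SAP*

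**What the plan says.** Protocol 11.4.3 (Overall Survival) treats three groups of subjects without a recorded death separately:

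- Withdrawal of consent: "Subjects who withdraw consent from the study will be censored at the time of withdrawal".
- Alive at the final cutoff: censored at the date last known alive.
- Lost to follow-up: "All subjects who are lost to follow-up before the 6-year data cutoff will be censored at the date they are last known to be alive".

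SAP 5.2.4.1 (Overall Survival, Definition) merges the first and third groups: subjects in either one "will be censored at the time of withdrawal or lost to follow-up". For the remaining group it says: "Subjects who are still alive at the cutoff date for the analysis will be censored at the last known alive". It then gives the derivation: "The date of last known alive will be determined by the maximum collection/assessment date from among selected data domains" in the clinical database.

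On follow-up, protocol 9.3.3 says that for subjects who have stopped study agent, "survival status will be assessed twice per year until the subject has been lost to follow-up", consent is withdrawn or the 6-year cutoff is reached. Protocol 10.3 requires the site to try to contact a lost subject and to document the attempts. Neither document says which date is recorded as the date of loss.

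SAP 5.2.4.2 reports the Kaplan-Meier curve, the median with 95% CI, and survival rates with 95% CI at 3, 4, 5 and 6 years.

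**The concern.** The two documents give different censoring rules for the same subjects on the same endpoint. The SAP does not mention or justify the difference. It is not a leftover from superseded text: the SAP uses the 6-year cutoff that Amendment INT-4 introduced, and the same amendment updated protocol 11.4.3.

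A subject should stay in the risk set only while a death would be known. If the loss date lies after the last evidence of life, the subject is counted as at risk and event-free over an interval in which vital status was not established. That pushes the survival estimates one way.

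Survival is a descriptive secondary objective in a single-arm study. However, Amendment INT-4 extended the study partly to report long-term survival under postmarketing commitments. With no test planned, the curve, median and yearly rates are themselves the result.

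**Working it through.** **1. Nothing to reproduce.** Neither document states an expected survival rate, event count or loss rate. The sample size (up to 75, protocol 11.2) is not a statistical calculation. The check therefore compares the two rules.

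**2. Where the rules differ.** Withdrawal of consent: same rule in both. Alive at cutoff: same rule in both. Lost to follow-up: last known alive in the protocol, time of loss in the SAP. Only lost subjects are affected.

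**3. Direction.** The Kaplan-Meier estimate is S(t) = ∏(1 − d_j/n_j) over death times up to t. Moving the censoring date of lost subjects later leaves every d_j unchanged and leaves each n_j equal or larger. Each factor therefore stays equal or rises, and so does S(t) at every t. The median can only stay equal or move later. If the two dates coincide, nothing changes.

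**4. Size, under assumptions.** None of the following is in the documents: true 6-year survival of 25%, 60%, 80% or 95%; 6-year loss of 5%, 10%, 20% or 40%; a gap of 0.5 or 1 year from last known alive to recorded loss; exponential death and loss times; administrative censoring uniform over 4–8 years. With 75 subjects and 1,500 simulated datasets per scenario, both rules were applied to the same data.

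A hand check uses a constant hazard. If the rule adds a fraction δ to person-time with the same deaths, the hazard is divided by (1 + δ), and the shift in S is about −S·ln(S)·δ. For S = 0.80 and δ = 6.3/382 = 0.0165, this is 0.80 × 0.2231 × 0.0165 = 0.0029, or 0.29 points.

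The last column is the simple binomial 95% half-width, 1.96·√(S(1−S)/75), which ignores censoring and so is on the narrow side.

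| True 6-year survival | Loss | Gap (y) | Added / observed person-years | Hand check (points) | Simulated shift (points) | Half-width (points) |
|---|---|---|---|---|---|---|
| 95% | 5% | 0.5 | 1.7/427 = 0.4% | 0.02 | +0.02 | 4.9 |
| 80% | 10% | 0.5 | 3.2/381 = 0.8% | 0.15 | +0.15 | 9.1 |
| 80% | 10% | 1.0 | 6.3/382 = 1.6% | 0.29 | +0.29 | 9.1 |
| 80% | 20% | 0.5 | 6.4/361 = 1.8% | 0.32 | +0.32 | 9.1 |
| 80% | 20% | 1.0 | 12.5/361 = 3.5% | 0.62 | +0.60 | 9.1 |
| 60% | 20% | 1.0 | 11.1/316 = 3.5% | 1.08 | +1.08 | 11.1 |
| 25% | 20% | 1.0 | 7.9/220 = 3.6% | 1.24 | +1.34 | 9.8 |
| 25% | 40% | 1.0 | 16.3/199 = 8.2% | 2.84 | +3.02 | 9.8 |

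In no simulated dataset did the later date give a lower estimate at year 3, 4, 5 or 6, as step 3 requires. The last-known-alive rule recovered the true value within simulation error. For loss of 5–20% the shift ran from 0.02 to 1.34 points. The last row is an extreme shown for scale.

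**The case against.** The strongest reply is that the SAP never says what the time of loss is. A reader might infer that it means the day the site stopped trying to reach the subject. The documents do not say so. If the date were programmed as the last contact, the two rules would coincide and there would be no bias. This stands, and it makes the upward shift conditional. It does not remove the problem: the next SAP sentence uses last known alive for a different group, so the natural reading is a different date, and an undefined censoring date needs correcting anyway.

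Second, a gap of 6 months or more cannot be assumed for every lost subject. Twice-yearly contact applies only after study agent stops. Subjects on treatment attend dosing visits every 3 or 6 weeks, so a loss during treatment need not leave a long gap. Nothing in the documents supports a figure of 12 months. This stands, and the 1-year rows are an upper assumption.

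Third, deaths in the gap are not necessarily missed. The contact efforts required by protocol 10.3 may uncover a death, which then counts as an event. If subjects are lost because they are dying, that is informative censoring, and the protocol's rule does not cure it either. Both points stand.

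Fourth, the simulation does not copy the SAP endpoint. The SAP clock starts in the parent study, and a subject had to be alive to enter the extension, so neither death nor loss in this study can occur in that early period. The figures are illustrations, not predictions.

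Finally, the effect is small beside the sampling error, and no test or decision is shown to depend on it. That limits the severity. It does not justify an unexplained departure from the protocol.

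**Conclusion.** The SAP is wrong as written on this point, and the severity is minor. The textual conflict is certain and concerns lost subjects only. The direction is certain if the recorded loss date is later than the last evidence of life, which is plausible for off-treatment subjects but not established. The size cannot be determined from the documents. With an assumed 5–20% lost and a gap of 0.5–1 year, 6-year survival rises by roughly 0 to 1.3 points, against a confidence half-width of about 5 to 11 points for 75 subjects.

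Two stronger readings go too far. One is that the SAP does bias survival upward; the documents support only that it can, depending on how the loss date is recorded. The other is that this rule alone makes the two documents' survival estimates differ. They also start the clock differently: protocol 11.4.3 at the first study siltuximab administration, SAP 5.2.4.1 at the first siltuximab or placebo treatment. That is a separate matter, which this correction does not settle.

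**What to change.** In SAP 5.2.4.1, split the merged sentence. Censor subjects lost to follow-up at the date last known alive, as in protocol 11.4.3, and state that the derivation already given there applies to them as well as to subjects alive at cutoff. When naming the data domains for that derivation, confirm that they hold only dates that are evidence of life and not the administrative date of loss.

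Leave the consent-withdrawal rule unchanged. Protocol and SAP agree on it, and adding a condition would create a mismatch where there is none.

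If the sponsor prefers to keep a loss date, the SAP should define it and give the reason for departing from the protocol.

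The cost is one sentence and a small change to the derivation program. No new data are needed, and study conduct is not affected.
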